7.1.1.2 Definition

- ◆ **Measurable disease** - the presence of at least one measurable lesion. If the measurable disease is restricted to a solitary lesion, its neoplastic nature should be confirmed by cytology/histology.
- ◆ **Measurable lesions** - *tumor lesions* that can be accurately measured in at least one dimension (longest diameter to be recorded) as ≥ 10 mm with MRI scan. Bone lesions are considered measurable only if assessed by CT scan and have an identifiable soft tissue component that meets these requirements (soft tissue component > 10 mm by CT scan). *Malignant lymph nodes* must be ≥ 15 mm in the short axis to be considered measurable; only the short axis will be measured and followed. All tumor measurements must be recorded in millimeters (or decimal fractions of centimeters). Tumor lesions situated in a previously irradiated area, or in an area subjected to other loco-regional therapy, are usually not considered measurable unless there has been demonstrated progression in the lesion.
- ◆ **Non-measurable lesions** - All other lesions (or sites of disease), including small lesions are considered non-measurable disease. Bone lesions without a measurable soft tissue component and leptomeningeal disease are non-measurable. Nodes that have a short axis <10 mm at baseline are considered non-pathological and should not be recorded or followed.

Target Lesions. Only the following lesions are eligible as target lesions:

- ◆ MRI contrast enhancing lesions with two perpendicular diameters of 10 mm or more visible on 2 or more axial slices which are 5 mm apart.
- ◆ Target lesion(s) must be measurable in two perpendicular diameters.

In most patients, only one lesion will be present. In case of multifocal disease, a minimum of 2 lesions and maximum of 5 largest enlarging lesions will be chosen as target and the sum of the products of the perpendicular diameters will be determined. All other lesions than target lesions, if applicable, are assessed according to the same schedule. They are only taken into account in two situations:

- ◆ If one of them clearly progresses, the overall response to therapy will be evaluated as "progression", independent of the response of target lesions
- ◆ All lesions must have completely disappeared to report a "complete response".

Adequate investigations must be carried out at each evaluation of the disease to detect eventual new lesions. If any new lesion is found, the response will be evaluated as "progression".

- ◆ By definition, non-target lesions are those that do not meet the criteria for target lesion. Measurements are not required but these lesions should be noted at baseline and should be followed as "present" or "absent".

All baseline evaluations should be performed as closely as possible to the beginning of treatment and never more than 4 weeks before the beginning of the treatment.

7.1.2 Tumor response evaluation

All patients will have their overall response (OR) from the start of study treatment until the end of treatment classified as outlined below:

Complete Response (CR): disappearance of all *target* and *non-target* lesions. Residual lesions (other than nodes < 10 mm) thought to be non-malignant should be further investigated (by cytology or PET scans) before CR can be accepted. Clinical evaluation must be stable or improving. No steroids should be needed.

Partial Response (PR): at least a 50% decrease in the sum of the product of perpendicular diameters of the target lesions, as compared to baseline. Non target lesions must be non-PD. Clinical evaluation must be stable or improving. Steroid dose must be stable or diminishing.

Stable Disease (SD): Neither sufficient shrinkage to qualify for PR nor sufficient increase to qualify for PD taking as reference the smallest tumor measurement recorded during the study. Clinical evaluation must be stable or improving. Steroid dose must be stable or diminishing.

Progressive Disease (PD): at least a 25% increase in the sum of products of perpendicular diameters of the measured lesions taking as references the smallest tumor measurement recorded during the study (including the baseline scan). Appearance of new lesions (including extracranial) will also constitute PD (including lesions in previously unassessed areas). In exceptional circumstances, unequivocal progression of non-target disease may be accepted as evidence of disease progression, where the overall tumor burden has increased sufficiently to merit discontinuation of treatment, for example where the tumor burden appears to have increased by at least 73% in volume (which is the increase in volume when all dimensions of a single lesion increase by 20%). Modest increases in the size of one or more non-target lesions are NOT considered unequivocal progression. If the evidence of PD is equivocal (target or non-target), treatment may continue until the next assessment, but on further documentation, the earlier date must be used. Worsening of the clinical evaluation should also be recorded as PD.

Table 1: Macdonald response criteria

	CR	PR	SD	PD
T1-Gd+	0	decrease \geq 50%	decrease $<$ 50% or increase $<$ 25%	increase \geq 25%
New Lesion	no	No	no	Yes*
Steroids	no	stable or decreasing	stable or decreasing	NA
Clinical evaluation	stable or improving	stable or improving	stable or improving	worsening
	All	All	All	Any

* including extracranial lesions

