- ◆ No known MRI or CT, including contrast media, contraindications
- ◆ Absence of any psychological, familial, sociological or geographical condition potentially hampering compliance with the study protocol and follow-up schedule; those conditions should be discussed with the patient before registration in the trial
- ◆ Before patient randomization, written informed consent must be given according to ICH/GCP, and national/local regulations.

Important note: All eligibility criteria must be adhered to, in case of deviation discussion with Headquarters and study coordinator is mandatory.

4 Trial Design

This is a randomized open label multicenter comparative phase II trial. The Korn design (Ref. 10) will be applied (for detailed statistical considerations see chapter 8).

[figure not shown]
Patients will be randomized at the EORTC headquarters after verification of the eligibility criteria (see chapter 3) to receive one of the following:

- ◆ Arm 1 (treatment): Trabectedin delivered as a 24-hour infusion every 3 weeks (day 1 of each 21-day cycle) at a starting dose of 1.5 mg/m² body surface area (BSA), until one of the treatment withdrawal criteria has been met.
- ◆ Arm 2 (control): Local standard of care.

For the trabectedin arm one cycle will be defined as 3 weeks.

For the control arm one cycle will be defined according to the treatment schedule of the chosen drug.

Disease will be assessed by the Macdonald response criteria (see chapter 7).

5 Therapeutic regimens, expected toxicity, dose modifications

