5.1 Therapeutic regimens

5.1.1 Experimental arm

Trabectedin will be given as a 24-hour infusion every 3 weeks at a starting dose of $1.5 \text{ mg/m}^2 \text{ BSA}$, until one of the treatment withdrawal criteria has been met. Subjects receiving trabectedin are required to receive dexamethasone pretreatment at 20 mg IV, 30 minutes before starting trabectedin.

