5.3 Initial dose and schedule

Trabectedin must be administered under the supervision of a physician experienced in the use of chemotherapy. Its use should be confined to personnel specialized in the administration of cytotoxic agents.

For this trial, the recommended starting dose is 1.5 mg/m² BSA, administered as an IV infusion over 24 hours with a 3-week interval between cycles. Administration through a central venous line is strongly recommended.

All patients must be premedicated with corticosteroids such as dexamethasone 20 mg IV, 30 minutes before each trabectedin infusion; not only as anti-emetic prophylaxis, but also because it appears to provide hepatoprotective effects. Additional anti-emetics may be administered as needed.

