6.3 During treatment

The following need to be performed on day 1 of each treatment cycle or within 72 hours before:

- ◆ Clinical examination (WHO PS, blood pressure, pulse rate, body weight, and body temperature).
- ◆ Assessment of all adverse events that have occurred since the previous visit and ongoing events from previous cycles should be followed.
- ◆ Complete blood counts to include hemoglobin, white blood cells, neutrophils, lymphocytes, platelets. For the experimental arm only, additional monitoring of hematological values should occur weekly during the first two cycles of therapy, and at least once between treatments in subsequent cycles
- ◆ A serum chemistry assessment to include at least creatinine, total bilirubin, ALT, AST, ALP, CPK, albumin, LDH, sodium, potassium, glucose, calcium. For the experimental arm only, additional monitoring of serum chemistry values should occur weekly during the first two cycles of therapy, and at least once between treatments in subsequent cycles
 - ◆ If ALP > 2.5 ULN, ALP hepatic isoenzyme 5-nucleotidase and/or GGT tests must be performed; ALP hepatic isoenzyme or 5-nucleotidase and/or GGT must be within the normal range.
 - ◆ Creatinine clearance will be calculated by Cockcroft and Gault formula (see Appendix E)
 - ◆ For the serum chemistry parameters not collected on the Serum Chemistry form: in case of abnormal value please record it as adverse event on the Adverse Event forms (grade, relationship, seriousness).
- ◆ Cranial MRI every 9 weeks from randomization and if clinically indicated
- ◆ Recording of corticosteroid dose every 9 weeks
- ◆ CT thorax/abdomen only if clinically indicated; if tumorous or unclear lesions detected repeat CT every 9 weeks and if clinically indicated
- ◆ HRQoL: QLQ-C30 (v3) and the BN-20 questionnaire: regardless the treatment arm, at week 3, week 6 and week 12 after treatment start (for more information see chapter 10).
- ◆ Pregnancy test (every two cycles)

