7.1.6 Best overall response

Best overall response is the best response designation recorded from the date of randomization until disease progression.

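### Read literally, the steroid condition for complete response cannot be met during trabectedin treatment, because every infusion carries mandatory dexamethasone; for partial response and stable disease the rule is ambiguous

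*Combined protocol and SAP*

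**What the plan says.** **Response rule (7.1.2 and Table 1).** For CR the text states "No steroids should be needed". For PR, and again for SD, it states "Steroid dose must be stable or diminishing". Table 1 shortens these to *no* for CR and to stable or decreasing for PR and SD, and its last row requires all conditions for each of the three. For progressive disease (PD) the steroid entry is NA. Overall response is assigned "from the start of study treatment until the end of treatment classified as outlined below". Section 7.1.6 uses a different window: "Best overall response is the best response designation recorded from the date of randomization until disease progression".

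**Premedication (5.1.1, 5.3, 5.7).** "Subjects receiving trabectedin are required to receive dexamethasone pretreatment at 20 mg IV, 30 minutes before starting trabectedin". Section 5.3 repeats this for every infusion and gives the purpose: "30 minutes before each trabectedin infusion; not only as anti-emetic prophylaxis, but also because it appears to provide hepatoprotective effects". Chapter 4 sets the interval: "For the trabectedin arm one cycle will be defined as 3 weeks". Section 5.4 sets no maximum number of cycles. Control treatment is the investigator's choice (5.1.2), with no mandated steroid.

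**Recording (6.1, 6.3).** Corticosteroid dose is recorded once before treatment and then on the instruction "Recording of corticosteroid dose every 9 weeks". Neither place says whether premedication is to be entered.

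**Use.** Best overall response, and the rate and median duration of objective response and of CR, are secondary endpoints (2.2). The two rates are reported with exact 95% intervals in the per protocol population (8.2.3.2). Table 11.1 carries the same steroid conditions into the preliminary RANO criteria.

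**The concern.** Two rules meet in one arm only. One makes the absence of steroids a condition of CR; the other obliges every trabectedin patient to receive a steroid at each cycle. The mandated dexamethasone is given for reasons unrelated to tumor symptoms, yet the response section does not set it aside.

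A site that applies Table 1 as printed would refuse CR to a trabectedin patient whose lesions had all disappeared. A site that sets premedication aside would grant it. Both could claim to follow the protocol. The trial is open label and response is assessed at the treating site (chapter 4, 7.1.1.1), so the choice may be made with knowledge of the arm. Any resulting misclassification would fall mainly on trabectedin. Durations are also exposed: under 7.1.7 they start when the response criteria are first met, so a response recognized late has a later start.

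**Working it through.** The plan states no figure on this point, so there is none to reproduce. The check sets the rules side by side and then shows the scale.

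**1. Exposure on schedule.** The response interval is 9 weeks (7.1.2.1), the trabectedin cycle is 3 weeks (chapter 4), and premedication is 20 mg per infusion (5.1.1).

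- Infusions per interval = 9 / 3 = 3
- Mandated dexamethasone per interval = 3 × 20 mg = 60 mg
- Before treatment the mandated amount is zero

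Without delays, the mandated amount is the same in every on-treatment interval, but higher than at the pre-treatment record.

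**2. Outcome under each reading, for a trabectedin patient with no steroid at baseline.**

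| Reading | CR during treatment | PR and SD during treatment |
|---|---|---|
| Premedication not counted | attainable | attainable |
| Counted; compared with the previous on-treatment assessment | not attainable | attainable (fixed dose is stable) |
| Counted; compared with the pre-treatment record | not attainable | not attainable |

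The documents do not choose between the rows. At the first 9-weekly assessment there is no earlier on-treatment assessment, so the second row helps only from the next one on.

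**3. A patient with no category.** In the third row, take a stable or shrinking scan with no new lesion and no clinical worsening. CR, PR and SD fail on steroids, and PD is not met. The not-evaluable category in 7.1.5 is for insufficient data, so it does not fit either.

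**4. Scale for the CR rate.** The planned per protocol trabectedin group is 57 (8.1.1). With zero responders the exact (Clopper-Pearson) lower limit is 0 and the upper limit is 1 − 0.025^(1/n):

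- 0/57: 0%, upper limit 1 − 0.025^(1/57) = 0.063, so 95% CI 0 to 6.3%
- 1/57: 1.8% (0.04 to 9.4%)
- 2/57: 3.5% (0.4 to 12.1%)

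The first line is what the literal rule yields if no CR is recorded outside treatment. The other two show what one or two disallowed CRs would have given. The documents state no expected CR rate, so the counts of one and two are illustrations, not forecasts.

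**5. Reach to the primary endpoint.** PFS counts first objective progression or death (7.1.3). The steroid entry for PD in Table 1 is NA, so the steroid rule neither creates nor removes a PFS event.

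**The case against.** The best defense is the wording of the CR sentence. It speaks of steroids being *needed* and stands beside lesion disappearance and clinical status, so it can be read as need arising from the tumor. Scheduled anti-emetic and hepatoprotective dexamethasone would then not count. This is a sensible reading, but Table 1 carries no such qualifier and nothing in the text makes the reading binding.

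Several stronger conclusions are tempting, and the documents do not support them:

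- *That response as a whole is barred on trabectedin.* A reader might infer this, but PR and SD fail only when premedication is counted and the comparison is with the pre-treatment dose.
- *That the CR rate is 0% by definition.* Section 7.1.6 runs to progression, and imaging continues after treatment stops without progression (6.4.3, 7.1.2.1), so a CR could be recorded once premedication has ended. The treatment-only window in 7.1.2 conflicts with this and is not reconciled.
- *That the 9-weekly record always falls on an infusion day and so shows an increase.* Imaging is timed from randomization, treatment may start up to 21 days later (chapter 6), and cycles may be delayed by up to 3 weeks (5.6.1.2). Section 6.3 allows the 72 hours before day 1, and the table in 6.5 places steroid recording in a separate 9-weekly column. A record may miss the premedication.
- *That blinded central readers will resolve the rule differently.* Section 16.6.1.4 says they review scans; it does not say they receive steroid doses.

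Two further points are fair. Section 7.1 calls its text a quick reference, and the imaging guidelines, CRF guidelines and review charter, which are not among the documents, may settle the matter. Control regimens may also include anti-emetic steroids, though only trabectedin mandates them. Neither point removes the gap in the protocol.

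**Conclusion.** The concern holds in limited form. Table 1 as printed makes CR unattainable in the trabectedin arm while treatment continues, and it imposes no corresponding bar on the control arm. PR and SD are left ambiguous, because no reference dose is given for judging stability.

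The effect is limited to best overall response, the objective response and CR rates and durations, and the RANO versus Macdonald tables in 11.2. Section 8.2.3.2 plans no between-arm test of response, so the harm is to descriptive estimates. A reader might infer that the primary comparison is biased too; it is not, since PFS and its event count do not depend on the steroid criterion.

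The size rests on two assumptions: that premedication is counted as steroid use, and, for the 0/57 figure, that no CR is credited after trabectedin stops. How many CRs would be lost cannot be estimated from the documents.

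**What to change.** In 7.1.2, Table 1, Table 11.1 and the 9-weekly steroid recording instruction, state for both arms that the steroid criterion refers to corticosteroid given for tumor-related symptoms and excludes protocol-mandated or anti-emetic premedication. Define the reference dose against which stable or diminishing is judged, including at the first on-treatment assessment; without this, PR and SD stay open to more than one reading. Carry the same wording into the CRF completion guideline so that the recorded dose matches the definition. It would also help to reconcile the response windows in 7.1.2 and 7.1.6.

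The cost is a few sentences and a line of CRF guidance. Sample size, schedule and primary analysis are untouched. Only the endpoint definition changes; the premedication stays as it is.

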7.1.2.1 Frequency of tumor re-evaluation

Cranial MRI every 9 weeks from randomization until progression.

CT thorax/abdomen only if clinically indicated; if tumorous or unclear lesions detected repeat CT every 9 weeks and as clinically indicated.

In the present study, tumors will be re-evaluated every 9 weeks during treatment. After discontinuation of protocol treatment, patients who have not progressed will still be re-evaluated every 9 weeks for the first year from randomization and every 12 weeks thereafter.

7.1.2.2 Date of progression

This is defined as the first day when the Macdonald response criteria for PD are met.

7.1.3 Progression Free Survival

Progression Free Survival (PFS) will be measured from the date of randomization until the date of first objective progression or the date of patient's death whichever occurs first. Patients without evidence of progression will be censored at the last follow-up visit date. If a patient received a second anti-tumoral therapy without prior documentation of disease progression, the patient will be censored at the date of starting new anti-tumoral therapy.

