5.7.1.2 Permitted medications

- ◆ The use of growth factors is permitted

6 Clinical evaluation, laboratory tests and follow-up

The schedule of evaluation as described below applies to both treatment arms. A treatment cycle is defined as 3 weeks in the experimental arm and 3 or 4 weeks in the control arm, whatever is more appropriate for the selected treatment. Disease evaluation (MRI and/or CT) should follow exactly the schedule described below, irrespective of the treatment arm.

Treatment should start within an acceptable delay from randomization. A maximum delay of 21 days is accepted.

6.1 Within 4 weeks prior to randomization and within 4 weeks prior to treatment start

All evaluations performed more than 28 days prior to treatment start must be repeated.

- ◆ Informed consent
- ◆ Medical history and demographics (age, gender, medical conditions at entry)
- ◆ Clinical examination (including WHO performance status, neurological examination, blood pressure, pulse rate, body weight, height and body temperature)
- ◆ Recording of corticosteroid dose
- ◆ Assessment of all adverse events
- ◆ Cardiac monitoring: 12-lead ECG, LVEF (MUGA or echo)
- ◆ Complete blood counts will be performed, to include hemoglobin, white blood cells, neutrophils, lymphocytes, platelets.
- ◆ A serum chemistry assessment to include at least creatinine, total bilirubin, ALT, AST, alkaline phosphatase (ALP), CPK, albumin, LDH, sodium, potassium, glucose, calcium, hepatic isoenzymes 5-nucleotidase (if applicable), GGT (if applicable).
 - ◆ Alkaline phosphatase $\leq 2.5 \times$ ULN; if alkaline phosphatase $> 2.5 \times$ ULN, ALP hepatic isoenzyme and/or 5-nucleotidase and/or gamma glutamyltransferase (GGT) must be within the normal range. Creatinine clearance will be calculated by Cockcroft and Gault formula (see Appendix E)
 - ◆ For the serum chemistry parameters not collected on the Serum Chemistry form: in case of abnormal value please record it as adverse event on the Adverse Event forms (grade, relationship, seriousness).
- ◆ A serum pregnancy test is required in women of reproductive potential within 72 hours prior to randomization (and also within 72 hours prior to treatment start). The pregnancy test is to be repeated during protocol treatment every two treatment cycles.
- ◆ HRQoL: QLQ-C30 (v3) and the BN-20 questionnaire (for more information see chapter 10).

6.2 Within 2 weeks prior to randomization and within 4 weeks prior to treatment start

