6.4.3 Until PD or start of new anticancer therapy

- ◆ Cranial MRI every 9 weeks and if clinically indicated
- ◆ Recording of corticosteroid dose every 9 weeks
- ◆ CT thorax/abdomen only if clinically indicated; if tumorous or unclear lesions detected repeat CT every 9 weeks or if clinically indicated
- ◆ Clinical examination (WHO PS only) every 9 weeks and as clinically indicated
- ◆ All ongoing adverse events should be followed every 9 weeks until resolution or stabilization.

HRQoL: QLQ-C30 (v3) and the BN-20 questionnaire at month 6 after treatment start for all patients regardless of treatment arm or progression status (see chapter 10).

Patient should be followed for survival every 9 weeks until PD or one year after randomization (whatever happens first) and every 12 weeks thereafter.

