7.1.4 Overall Survival

Overall Survival (OS) is calculated from the date of randomization up to the date of death (any cause). For patients still alive or lost to follow-up at the time of analysis, survival will be censored at last follow-up visit date.

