7.1.5 Overall response

All patients included in the study must be assessed for response to treatment, even if there is a major protocol treatment deviation or if they are ineligible, or not followed/re-evaluated. Each patient will be assigned one of the following categories: complete response, partial response, stable disease, progressive disease, early death or not evaluable. Early death is defined as any death occurring before the first per protocol time point of tumor re-evaluation.

Patients' response will be classified as "not evaluable" if insufficient data were collected to allow evaluation per these criteria.

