7.1.7 Response duration

Objective response duration (CR/PR) and complete response (CR) will be measured similarly to PFS (see above) but starting from the time measurement criteria for CR/PR or CR (whichever is first recorded) are first met.

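### PFS is censored at the last follow-up visit instead of the last tumor assessment, so the primary comparison can shift if one arm loses more scans than the other

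*Combined protocol and SAP*

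**What the plan says.** Section 7.1.3 (PFS): "Patients without evidence of progression will be censored at the last follow-up visit date". Its next sentence censors a patient who starts another anti-tumoral therapy without documented progression at the start date of that therapy. Section 7.1.4 (OS) uses the same anchor: "survival will be censored at last follow-up visit date". Section 8.2.3.1 describes the primary Cox model and adds no censoring rule.

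Scans follow their own clock. Section 7.1.2.1 asks for "Cranial MRI every 9 weeks from randomization until progression". Clinic visits on treatment are more frequent. Chapter 6 states "A treatment cycle is defined as 3 weeks in the experimental arm and 3 or 4 weeks in the control arm", and section 6.3 opens with "The following need to be performed on day 1 of each treatment cycle or within 72 hours before". Section 6.4.3 lists survival as a follow-up item: "Patient should be followed for survival every 9 weeks until PD or one year after randomization", and every 12 weeks after that.

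For response, section 7.1.5 classes a patient as not evaluable "if insufficient data were collected to allow evaluation per these criteria". PFS has no counterpart. Response duration (7.1.7) and the RANO/Macdonald PFS comparison (11.2) take over the PFS definition. Section 8.2.4 plans no sensitivity analysis.

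**The concern.** A last-visit date suits OS, because vital status is known at any contact. Radiological progression is known only when a scan is done. If a patient attends cycle visits, or a follow-up visit at which the MRI is missed, the visit rule keeps that patient in the risk set as progression-free over time in which radiological progression could not be seen.

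If both arms lose scans equally, PFS-6 is overstated in both and power may fall slightly. If one arm loses more, its hazard is understated and the treatment HR moves in its favor: more false positives if that arm is trabectedin, less power if it is control. The comparison is small (57 vs 29 patients) and tested at one-sided 10%, so a few unseen progressions matter. With no sensitivity analysis planned, the effect would not show in the planned outputs.

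**Working it through.** **Inputs from the plan.** PFS-6 15% control and 35% trabectedin, exponential PFS, 2:1 allocation, one-sided 10%, power 85%, 72 events, 86 patients (57/29), stepped accrual (8.1.1); analysis at 71 events (8.2.3.1); futility stop if HR ≥ 1 at 36 events (8.3); MRI every 63 days (7.1.2.1).

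**Plan's own figure.** HR = ln(0.35)/ln(0.15) = 0.5534. Schoenfeld events = (1.2816 + 1.0364)² / [(2/3)(1/3)(ln 0.5534)²] = 5.373/(0.2222 × 0.3501) = 69.1, so 70. With the futility look, 72 events give 85.2% power at HR 0.55, which accounts for the stated 72. The fix moves censoring dates, so this requirement does not change.

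**One patient (assumed course).** Scanned on day 63, misses the MRIs due on days 126 and 189, attends 21-day visits to day 210 with no worsening noted. The visit rule censors at day 210, the last-scan rule at day 63: 147 days (4.83 months) differ. The planned control hazard is -ln(0.15)/6 = 0.316 per month, so the chance of a PFS event in that window is 1 - exp(-0.316 × 4.83) = 78%. At the trabectedin hazard, 0.175, it is 57%.

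**Simulation.** 86 patients, accrual as in 8.1.1, analysis at 71 events, progression dated at the next 63-day scan, visits every 21 days, log-rank test at one-sided 10%, 10,000 runs per scenario (standard error about 0.3-0.5 point; PFS-6 from 2,000 runs). The following are assumptions, not in the documents: the dropout rates; dropouts stop scans at day 30 or 93 and stay in contact 3-10 more months; death comes on average 6 months after progression and counts while in contact; 0%, 50% or 90% of missed progressions are recorded clinically, one 9-week visit late. Ranges cover those three shares.

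| Scan dropout, trabectedin/control | Quantity | Visit rule | Last-scan rule |
|---|---|---|---|
| 0%/0% | type I error | 10.4% | 10.4% |
| 5%/0% | type I error | 12.1-13.3% | 10.6-10.8% |
| 10%/5% | type I error | 12.1-13.1% | 10.3-10.7% |
| 10%/10% | type I error | 10.4-11.0% | 10.3-10.8% |
| 10%/10% | control PFS-6 | 27.0-27.9% | 24.9-25.0% |
| 0%/0% | power | 85.5% | 85.4% |
| 10%/10% | power | 82.8-84.9% | 84.2-84.6% |
| 5%/10% | power | 80.8-82.7% | 85.0-85.9% |
| 20%/5% (illustrative) | type I error | 15.0-20.3% | 9.3-10.2% |
| 0%/20% (illustrative) | power | 67.3-76.4% | 85.9-86.5% |

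At 10%/5%, 0.10 × 57 + 0.05 × 29 = 7.2 patients stop scans, and about 5 of the 86 have a progression not seen on a scan. The mean null HR is 0.97-0.98 under the visit rule and 1.00 under the last-scan rule. PFS-6 exceeds the 15% input under both rules because progression is dated at the next scan; only the gap of 2-3 points belongs to the censoring rule.

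**Checks at 10%/5%, type I error unless stated.**
- Planned adjusted Cox Wald test (three binary factors, assumed HR 1.5 each, 4,000 runs): 13.9-15.0% vs 12.7-13.1%. The same test gives 12.0% vs 12.1% with no dropout, so about 1-2 points belong to the rule. Power at 5%/10%: 79.8-82.6% vs 83.7-83.9%.
- With the futility look: 11.5-12.4% vs 9.8%.
- Mean time from progression to death 3-12 months: 10.9-13.9% vs 10.0-10.5%.
- Scans stopped because of progression: 13.1-15.0% vs 12.4-12.6%.

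**A different dropout model.** Rates per scan visit, data cut at 21.5 months, treatment-only Cox. At 10% trabectedin / 2% control per visit, null rejection is 28.2% vs 14.5% with no clinical capture, and 15.6% vs 11.7% with half captured. Per-visit rates compound: if permanent, 1 - 0.90³ = 27% against 1 - 0.98³ = 6% after three scans. That is a far larger imbalance than 10%/5% overall.

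**The case against.** The case for leaving the rule alone is substantial.

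- Unscanned time is not simply credited as progression-free. Section 7.1.2 records clinical worsening as progression, examinations take place every cycle (6.3), and death is an event. A reader might infer that no event can occur without a scan; the documents do not say that. What remains exposed is radiological progression without recorded worsening. Section 7.1.3 also speaks of objective progression, so full clinical capture is not assured.
- A reader might infer from the separate survival item in 6.4.3 that off-treatment patients are routinely seen between scans. Before progression they are not: survival follow-up and off-treatment MRI (7.1.2.1) are both every 9 weeks in the first year and every 12 weeks after that. The exposure lies in on-treatment cycle visits and in follow-up visits at which the MRI is missed.
- Scans continue despite treatment delays (6.3.1), and missing scans are queried (16.6). A query cannot recover a scan that was never done.
- Only about 86 - 71 = 15 patients are censored at the planned analysis, and at moderate imbalance the shift is about 1-3 points. This stands, and it limits the weight of the point.
- Last-scan censoring is no full cure. It gains little when patients stop scans because they are progressing, and under the per-visit model the null HR still averages 0.95 (visit rule 0.84) at 10% trabectedin / 2% control with no clinical capture. This also stands.

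**Conclusion.** The point holds as a conditional risk. The primary endpoint uses the OS censoring anchor, nothing overrides it, and time under observation without scans can enter the PFS risk set. With full scan compliance there is no measurable difference, and with equal dropout type I error holds. At assumed dropout of 10%/5% the false-positive rate is 1-3 points higher than under last-scan censoring; at 5%/10% power is 2-5 points lower by log-rank. Larger shifts need more unequal dropout.

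A reader might infer that the primary HR is biased, or biased toward trabectedin. The documents do not support either: they give no rate or direction of scan dropout, and the open-label design alone supplies neither. The sizes rest on the assumed dropout rates, length of contact after the last scan, time to death and clinical capture. The case for changing the rule is that the change is cheap and should be settled before the data are seen. It is a worthwhile improvement, not a defect that invalidates the design.

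**What to change.** In 7.1.3:

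1. Censor patients without documented progression or death at the date of the last adequate tumor assessment, or at randomization if there is none.
2. Define adequate as an assessment at which the Macdonald criteria of 7.1.2 (Table 1) could be applied to give CR, PR, SD or PD. CR, PR and SD require every row of Table 1, so a visit without MRI cannot qualify as progression-free. The not-evaluable category of 7.1.5 will not serve here, because it is assigned per patient and not per scan.
3. Use the same anchor in the new-therapy sentence: the last adequate assessment on or before the start of new anti-tumoral therapy. Otherwise a patient who stops scans and later changes therapy keeps the unscanned time. The simulation does not include this case, so no size is attached to it.
4. Count progression or death on its own date in the primary analysis, and keep the last follow-up visit as the anchor for OS only.

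In 8.2.4, pre-specify two sensitivity analyses: (a) the current visit-date and new-therapy-date rule; (b) censoring at the last adequate assessment when progression or death follows two or more consecutive missed scans. Rule (b) should stay a sensitivity analysis, because it distorts the test when dropout is very unequal (type I error 8-9% at 20%/5%, 14% at 0%/20%). Sections 7.1.7 and 11.2 inherit the change.

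The cost is a few sentences, two extra model runs and slightly shorter censored follow-up. No new data are needed, since scans are already collected centrally (16.6), and the event target does not change.
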